3.1.4. Safety Assessments

Safety will be monitored at regular intervals throughout the study by means of laboratory tests and clinical visits as reported in Schedule of Activities (SOA) ([Table 1](#)) and in [Section 7.1](#), Safety Assessments.

3.1.5. Efficacy Assessments

Anti-tumor activity will be assessed through radiological tumor assessments conducted at baseline and on treatment every 8 weeks ± 7 days starting from Cycle 1 Day 1 up to 1 year, then every 3 months (± 7 days) as specified in the SOA [Table 1](#). In addition, radiological tumor assessments will also be conducted whenever disease progression is suspected (eg, Symptomatic deterioration), and at EOT (if not done in the previous 8 weeks) and during follow up visits (if applicable). Assessment of response will be made using RECIST version 1.1 ([Appendix 2](#)) and irRC ([Appendix 3](#)). Further details are provided in [Section 7.2](#), Tumor Assessments.

3.1.6. Pharmacokinetic (PK)/Immunogenicity Assessments

PK/Immunogenicity sampling will be required for all patients (See [Table 2](#)) and [Section 7.3](#) and [7.5](#) for further details). The proposed PK timepoints may be reconsidered and amended during the study based on the emerging safety and PK data. No drug interaction is anticipated between PF-05082566 and mogamulizumab. Since PF-05082566 and mogamulizumab are eliminated via a non-specific catabolic degradation process, it is unlikely that concomitant medication can alter its clearance even if target expression is affected. To assess any potential interactions, steady state PK and the formation of anti-drug antibodies (ADA) will be monitored for both agents and compared with historical data.

CC1

Approximately 70 patients are expected to be enrolled in the study overall (including dose-finding and expansion cohorts).

3.1.8. Starting Dose Selection Strategy

In the ongoing First-In-Human Phase 1 Study B1641001, PF-05082566 as single agent has been well tolerated up to the dose of 10 mg/kg (the highest planned dose level), with only 1 DLT reported (Grade 3 alkaline phosphatase (ALP) increase at 0.06 mg/kg), which was not observed at higher dose levels and upon review was determined by two Pfizer safety review committees to be related to disease progression. No further DLTs have been reported.

However, in order to minimize the potential risk of synergistic toxicity due to the combination, the starting dose for PF-05082566 in this study will be set to 1.2 mg/kg. Exposure at 1.2 mg/kg is above the projected efficacious concentration and safety data supports this starting dose, as there were no severe PF-05082566 related AEs at this dose and at higher doses.

The starting dose of mogamulizumab will be 1 mg/kg. The dose selected for this study is the dose approved for the treatment of relapsed or refractory CCR4 positive ATL, PTCL and CTCL. This dose administered weekly for 4 weeks and then every other week (ie, biweekly) until disease progression, appeared to be safe in clinical trials conducted in more than 152 ex-Japan patients with T cell lymphoma and in more than 800 patients with ATL. The AEs reported have generally been mild to moderate in severity, with the most frequent mogamulizumab-related TEAEs being infusion related reaction, nausea, pyrexia, fatigue, and drug eruption, all easily manageable through the administration of specific treatment.

3.1.9. Criteria for Dose Escalation

No dose escalation of mogamulizumab is foreseen for the estimation of the combination MTD. Dose escalation and de-escalation of PF-05082566 will follow the Time-to-Event Continual Reassessment Method (TITE-CRM)^[28,33] up to 5 mg/kg.

A flat dosing of PF-05082566 100 mg will be studied to confirm the safety and PK at a dose that may be used for the expansion cohorts. The safety data at 100 mg flat dose (equivalent to 1.2 mg/kg) will be pooled together with the data at 1.2 mg/kg in the TITE-CRM model.

The 5.0 mg/kg cohort (if safe and tolerable) will enroll at least 6 squamous NSCLC patients to determine RP2D.

In each cohort, 3 to 9 patients evaluable for MTD determination may be enrolled.

The first 3 patients (Dose Level 1) will be treated at the starting dose. For each subsequent patient, the probability of DLT is estimated for each level based on all the collected data from all treated patients up to that time and the prior expectations of toxicity, and the patient is assigned to the currently estimated target level (with escalation restrictions as indicated below), defined as the dose having an estimated probability of DLT closest to but not greater than the target rate (30%).

The probabilities of toxicity are estimated based on a Bayesian statistical model to learn about the overall dose-toxicity relationship.

Patients' DLT data will be reported to the study statistician who will update the dose-toxicity model before the next enrolled patient is treated.

The MTD is defined as the highest combination dose with a DLT rate <30% from the model estimate (see [Section 9.2](#)).

Dose escalation may stop if:

- Maximum sample size (n=30, see [Section 9.2](#)) is reached; or
- 9 DLT evaluable patients have been treated at the estimated MTD (6 if no DLT observed at any dose); or
- All doses appear to be overly toxic and the MTD cannot be determined in the current trial.

In the TITE-CRM paradigm, patients who have enrolled in the trial, but have not experienced DLT, will be included in the probability calculation with an initial weight equal to the proportion of the 8-week (2 cycles of PF-05082566 and mogamulizumab) DLT observation period that the patients have completed (however, the weight function may be modified if accumulating safety data suggest a different pattern).

Patients who experience DLT or complete the observation period without DLT will be assigned full weight (=1).

Details on the TITE-CRM method are provided in [Section 9.2](#) and the Statistical Analysis Plan (SAP).

To avoid overly rapid escalation and to retain the efficiency of dose administration when enrollment is fast, the following restrictions and practical considerations will be followed.

- Dose skipping in escalation to untested doses is not allowed ($k \rightarrow k+1$). In particular, at least three patients should have been treated at dose level k before escalation to dose level $k+1$;
- At least three patients should have been on treatment (for a minimum of 3 weeks) and observed DLT rate <33% at dose level k before a patient is assigned to dose level $k+1$ (*Note that the waiting window depends on our knowledge in the time-to-event pattern of toxicity and accumulating safety data, and thereby the confidence in the associated weights. However, intentional delay in enrollment in the absence of DLT or serious AEs should be minimized and discouraged*);
- Dose escalation recommendation by the TITE-CRM algorithm may be overruled by the Sponsor if the nature of the existing data causes safety concern.

Dose escalation and de-escalation will be carried out according to [Table 6](#).

Table 6. Dose Escalation and De-Escalation Cohorts

Dose Levels	PF-05082566 Doses* (mg/kg)	Mogamulizumab Doses (mg/kg)
Dose Level 3	5	1
Dose Level 2	2.4	1
Dose Level 1a**	100 mg flat dose	1
Dose Level 1 (starting dose)	1.2	1
Dose Level -1	1.2	0.5
Dose Level -1a***	50 mg flat dose	1

* Intermediate dose levels could be used for dose de-escalation based on DLTs observed.

** This cohort can be dosed simultaneously with any other dose cohort..

*** To be used for dose reductions for those on the 100 mg flat dose cohort.

Occurrence of DLTs during the exploration of Dose Level (DL) 1 will require reduction of mogamulizumab to 0.5 mg/kg (ie, DL -1). If Dose Level -1 is tolerated with no DLTs, then dose escalation of PF-05082566 will continue according to the table above, maintaining mogamulizumab at 0.5 mg/kg until an MTD is reached and/or the PF-05082566 dose is escalated to the highest planned dose of 5 mg/kg.

Intra-patient dose escalation will not be permitted.

Cumulative safety data will continue to be evaluated at the estimated MTD in the expansion cohorts using the Bayesian statistical model. Should emerging data in the expansion cohorts indicate that the selected dose is more toxic than previously estimated (DLT rate >30%) or in case of exposure plateau **CC1**

For the first dose-finding cohort, a minimum 7-day time window between the first doses of subsequent patients will be applied. For the following dose-finding cohorts, a minimum 24-hour time window between the first doses of the first 3 patients will apply. A 24 hr time window between dosing is not necessary between cohorts dosed simultaneously.

At a given dose level, a time window between first doses will not be required after the treatment of the first 3 patients.

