3.1.2. Dose Expansion portion

Once the MTD of PF-05082566 administered in combination with mogamulizumab has been estimated with confidence, expansion cohorts of patients will be enrolled to further study the safety, tolerability, PK/PD, and preliminary anti-tumor activity for PF-05082566 in combination with mogamulizumab, as well as to study [CC1](#)

Tumor types for the expansion cohorts will be selected from CRC, bladder, ovarian, squamous esophageal, SCCHN and/or squamous NSCLC. Dose, final tumor types, [CC1](#) for these cohorts will be selected based on emerging data from the dose-finding portion of the study or obtained from ongoing studies testing PF-05082566.

The total enrollment into all expansion cohorts will be up to 40 response-evaluable patients.

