9.1. Analysis sets

1. Full analysis set.

The full analysis set includes all enrolled patients.

2. Safety analysis set.

The safety analysis set includes all enrolled patients who receive at least one dose of study medication.

3. DLT evaluable set.

All enrolled patients who are eligible for the study and receive study treatment. Note that every patient will contribute to the determination of the MTD including patients who are lost to follow-up prior to completion of the 2 cycles' DLT observation period.

4. PK/Immunogenicity and PK parameter analysis sets.

The PK/ADA concentration population is defined as all enrolled patients who have been treated and have at least one post dose concentration measurement of either PF-05082566 or mogamulizumab.

The PK parameter analysis population is defined as all enrolled patients who have been treated and whose concentration-time data allows the estimation of at least 1 of the PK parameters of interest.

5. **CCI**

6. ECG/QTc Analysis set.

Treated patients who have baseline and at least 1 on study ECG/QTc measurement.

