9.3. Sample Size Determination

Due to the dynamic nature of the Bayesian allocation procedure, the sample size of the TITE-CRM approach cannot be determined in advance. The maximum sample size is set as 30 for dose escalation cohorts in order to have a reliable and accurate estimate of the MTD based on simulation results. Based on probability theory, a sample size of 30 will ensure the estimates of any binary variable (eg, objective response rate) have a 95% confidence interval of width <0.36. A sample size of 30 also enables the detection of any unexpected toxicity that occurs at 5% rate (in a non-dose-dependent fashion) with a probability of 0.79, and that occurs at 10% rate with a probability of 0.96.

A stopping rule (see [Section 3.1.9](#)) will also be implemented for possible early stopping if there is strong confidence in the estimated MTD.

Additional patients will be required for expansion cohorts. The total number of patients in expansion cohorts will be determined based on emerging data from this study, cancer indication, and the patient population of interest.

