4.3. Other Analysis Set

4.3.1. DLT-evaluable Set

[figure not shown]
The DLT-evaluable set includes all enrolled patients who are eligible for the study and receive study treatment. Note that every patient will contribute to the determination of the MTD including patients who are lost to follow-up prior to completion of the 2 cycles' DLT observation period.

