5. GENERAL METHODOLOGY AND CONVENTIONS

5.1. Hypotheses and Decision Rules

5.1.1. Hypotheses and Sample Size Determination

No formal statistical hypothesis testing is planned.

Due to the dynamic nature of the Bayesian allocation procedure, the sample size of the TITE-CRM approach cannot be determined in advance. The maximum sample size is set as 30 for dose escalation cohorts in order to have a reliable and accurate estimate of the MTD based on simulation results. Based on probability theory, a sample size of 30 will ensure the estimates of any binary variable (eg, objective response rate) have a 95% confidence interval (CI) with width <0.36. A sample size of 30 also enables the detection of any unexpected toxicity that occurs at 5% rate (in a non-dose-dependent fashion) with a probability of 0.79, and that occurs at 10% rate with a probability of 0.96.

A stopping rule will also be implemented if:

- Maximum sample size (n=30) is reached; or
- 9 DLT evaluable patients have been treated at the estimated MTD (6 if no DLT observed at any dose); or
- All doses appear to be overly toxic and the MTD cannot be determined in the current trial.

Additional patients will be required for expansion cohorts (N=40). The total number of patients in expansion cohorts will be determined based on emerging data from this study, cancer indication, and the patient population of interest.

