6.1. Primary Endpoints

6.1.1. DLT

6.1.1.1. Primary Analysis

The primary analyses will be based on the DLT-evaluable set. DLTs will be listed and summarized by treatment group.

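### Does the plan need to fix how much DLT follow-up must stand behind the MTD that opens expansion?

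*Protocol*

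**What the plan says.** Protocol 3.1.9 lists three conditions under which escalation may stop. One is that "9 DLT evaluable patients have been treated at the estimated MTD (6 if no DLT observed at any dose"). Protocol 9.1 defines the DLT evaluable set as "All enrolled patients who are eligible for the study and receive study treatment", and SAP 4.3.1 agrees: "The DLT-evaluable set includes all enrolled patients who are eligible for the study and receive study treatment". Both add that patients lost before the two cycles end still contribute. A patient without a DLT enters the model with weight equal to the fraction of the 8-week window completed, and the MTD is the highest dose whose modelled DLT rate is below 30%.

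The only explicit minimum follow-up is in 3.1.9: "At least three patients should have been on treatment (for a minimum of 3 weeks"). It governs moving from level k to k+1.

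Expansion has a separate condition. Under 3.1.2, once the MTD "has been estimated with confidence, expansion cohorts of patients will be enrolled". Protocol 9.3 describes the stopping rule as being "for possible early stopping if there is strong confidence in the estimated MTD". Neither expression of confidence is given a number.

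The SAP adds no reading rule. For the primary endpoint, 6.1.1.1 says "DLTs will be listed and summarized by treatment group". SAP 2 sets the primary cut-off at 24 months after the last patient's first dose, and SAP 7 plans no formal interim analysis.

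**The concern.** Taken together, these passages allow a literal reading in which the ninth patient (or the sixth, with no DLT anywhere) is dosed, the count is met, the model is read that day and expansion opens. Some patients at the candidate MTD would then have little or no follow-up. The protocol chose TITE-CRM because toxicity of a combination may come late, so a reading taken on thin follow-up seems to work against the reason for the design.

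At stake is the dose given to expansion patients treated in roughly the next 8 weeks: 8 patients at one per week, 4 at one per 2 weeks, and more if they enter together, as Protocol 3.5 allows. Expansion may take up to 40 response-evaluable patients. The exposure arises only if expansion uses the model MTD. Protocol 3.4 also allows a lower dose and 3.5 a 100 mg flat dose.

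**Working it through.** **The plan's own figures.** The documents give no operating characteristic for the 9/6 rule. The nearby figures in Protocol 9.3 reproduce: 1 − 0.95^30 = 0.785 (stated 0.79) and 1 − 0.90^30 = 0.958 (stated 0.96).

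**Can the reading time change the answer?** Model from Protocol 9.2: F_i(β) = p_i^exp(β), β ~ N(0, 1). A DLT contributes F, and a patient without one contributes 1 − wF. The posterior mean of β is plugged in. Assumptions: three patients at each of Dose Levels 1 and 2 complete without DLT; skeleton for Levels 1 to 3 is 0.186, 0.300, 0.422 (in brackets 0.095, 0.186, 0.300), taken from the example behind Figure 3.

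- Six patients just dosed at Level 3, all w = 0: Level 3 estimate 0.107 [0.074], so the MTD reads as Level 3.
- The same six after 8 weeks with 3 DLTs: 0.334 [0.319], so Level 2.
- Nine at Level 3, 2 DLTs, seven at w = 0: 0.368 [0.346], so Level 2.
- The same nine, all complete, still 2 DLTs: 0.198 [0.186], so Level 3.

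An early reading can therefore err either way. On the six-patient branch, with a true DLT rate of 40% and uniform onset, P(no DLT seen in 6) = (1 − 0.4t/8)^6. This is 1.00 at first dose, 0.377 at t = 3 weeks and 0.047 at t = 8 weeks.

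**How often, and what does waiting gain?** Simulated trials that stop on the count; linear weights and uniform onset unless stated; one patient per week unless stated. True rates: A = (0.10, 0.20, 0.45), B = (0.05, 0.10, 0.20). Arrows run from the reading at the count to the same model after full follow-up. A dash means not reported, or no dose above 30%.

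| Setting | MTD differs | Correct dose | Dose above 30% chosen |
|---|---|---|---|
| A | 30% | 40% → 48% | 32% → 26% |
| B | 11% | 74% → 77% | – |
| A, one per 2 weeks | 25% | 50% → 52% | 29% → 29% |
| B, one per 2 weeks | 9% | 78% → 81% | – |
| A, Cycle 2 onset, matched weights | 41% | – | 38% → 28% |
| A, Cycle 1 onset, matched weights | 27% | – | 30% → 28% |
| A, Cycle 1 onset, linear weights | 24% | – | 20% → 26% |
| Rates (0.03, 0.06, 0.10) | 4% | – | – |
| Rates (0.02, 0.03, 0.05) | 1% | – | – |

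Repeat runs of A at one per week gave 46% → 51% (reading one week later) and 41% → 46%. Together with the table, the gain is 5 to 8 points. At one per 2 weeks a repeat gave 50% → 49% correct and 27% → 28% over-toxic. In the two low-rate rows the full-follow-up dose was lower in at most 0.1% of trials.

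**In patients.** Of the first 8 expansion patients in A, the mean number on the 45% dose falls from 2.1 to 1.95 (0.15 of a patient) if the model is updated before each one. It falls from 2.6 to 2.05 (0.55) if the dose is frozen at the first reading. Freezing does not match Protocol 3.1.9 and 3.3, which keep feeding expansion data into the model and provide for a change if the DLT rate proves higher than expected.

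**Does the text force the early reading?** No. Stopping is permissive in 3.1.9 and tied to confidence in 9.3. The expansion condition in 3.1.2 is separate from the count. Protocol 3.1.9 has the statistician refresh the model ahead of each new patient, which can naturally include the first expansion patient. Protocol 9.7 gives DLT review to a Dose Escalation Steering Committee with its own charter.

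**The case for a change.** The best case for a change is that it costs only wording. The count, the weights and dose-finding accrual would stay as they are, no patients are added, and the rule for opening expansion would be written down beforehand. No spacing is required at a level after its first three patients, so patients four to nine could be dosed close together and carry little weight. With late onset the over-toxic choice in A falls from 38% to 28%, even with weights matched to the true onset. Having a model refreshed before each patient does not set a minimum follow-up.

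What stands: no visible passage sets that minimum, and with fast accrual, late onset and a truly toxic top dose the timing matters. What does not stand is the step from silence to a defect. Reading the MTD at the moment of the last first dose is a worst case that the plan nowhere prescribes. Waiting is also a trade-off, since Protocol 9.2 adopts TITE-CRM to keep accrual open and 3.1.9 asks that deliberate enrolment delay be minimized when there are no DLTs or serious AEs. Scenario A is pessimistic beside the single-agent record in the protocol: one DLT with PF-05082566 up to 10 mg/kg, later attributed to progression (3.1.8), and one DLT patient among 16 on mogamulizumab (1.2.5.1). Combination rates are unknown, so this weakens A without excluding it.

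The stopping verb might also seem to differ, since SAP 5.1.1 says "A stopping rule will also be implemented if" where Protocol 3.1.9 is permissive. Protocol 9.3 itself says the rule will be implemented, "for possible early stopping if there is strong confidence in the estimated MTD". The SAP sentence is a shortened form of that, so the difference is editorial.

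**Conclusion.** No change follows. The plan leaves the follow-up behind the expansion-opening MTD unwritten, but the team has what it needs to settle it sensibly: a condition for expansion distinct from the stopping count, a model updated as data arrive, continued modelling in expansion, and committee review. How long to wait is a sponsor judgement. The cost is up to 8 weeks. The gain in correct selection is 5 to 8 points in scenario A at one patient per week and 3 in B. At one per 2 weeks it lies between −1 and +2 points in A, with no reduction in over-toxic selection; B gains 3 points but has no over-toxic dose to avoid. One onset pattern favours not waiting.

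These figures rest on the example skeleton, assumed true rates and assumed accrual. The adaptive cyclical weight, the Dose Level −1 path and the minimum of six squamous NSCLC patients at 5 mg/kg were not modelled. The committee's charter and the cited method papers were not available, and the end of the expansion rule in 3.1.9 is redacted, so a reading rule may already exist there.

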3.3. MTD Definition

The MTD is defined as the highest combination dose with a DLT rate $<30\%$ from the TITE-CRM model estimate (see details in [Section 9.2](#)).

Once the MTD is estimated, additional patients may be enrolled at this dosing level. In the expansion cohort, patients' DLT data will be entered into the Bayesian statistical model of the TITE-CRM procedure. If the posterior distribution of the model incorporating the additional data from the expansion cohort suggest the estimated MTD is associated with a higher than expected DLT rate the next lower dose or an intermediate dose level will be expanded, and may be declared as the RP2D.

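### The mogamulizumab step-down at Dose Level 1 has no stated DLT count or precedence, and the 0.5 mg/kg branch it opens has combinations for which the model-defined MTD cannot be estimated

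*Protocol*

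**What the plan says.** **Allocation rule.** Protocol 3.1.9 says: "For each subsequent patient, the probability of DLT is estimated for each level based on all the collected data from all treated patients". The patient then goes to the level whose estimate is nearest to 30% without exceeding it. Patients without a DLT enter with "an initial weight equal to the proportion of the 8-week" window completed. Escalation also needs at least three patients "on treatment (for a minimum of 3 weeks) and observed DLT rate" below 33%. Section 3.3 adds: "The MTD is defined as the highest combination dose with a DLT rate" under 30% from the TITE-CRM estimate. Section 9.7 bases dosing guidance on that model.

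**Step-down.** The same section 3.1.9 says: "Occurrence of DLTs during the exploration of Dose Level (DL) 1 will require reduction of mogamulizumab to 0.5 mg/kg" (Dose Level -1). It gives no number of DLTs, no denominator and no reference to the model. Protocol 9.2 and SAP 5.1.2 say only that 0.5 mg/kg is a possibility if the starting dose proves intolerable, a term neither defines.

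**Branch.** "If Dose Level -1 is tolerated with no DLTs, then dose escalation of PF-05082566 will continue according to the table above". Throughout that escalation mogamulizumab stays at the halved dose, and PF-05082566 may climb as far as its planned maximum of 5 mg/kg unless an MTD comes first.

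**Levels.** Table 6 has one row with mogamulizumab 0.5 mg/kg, Dose Level -1 (1.2+0.5). Dose Levels 2 and 3 are 2.4+1 and 5+1. Section 9.2 lists levels by PF-05082566 dose (1.2, 2.4, 100 mg flat, 5.0 mg/kg) and uses four prior rates p_i with no printed mapping. SAP 3.4.1 and 5.2 define five treatment groups: Dose Levels -1, 1, 1a, 2 and 3.

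**The concern.** There are two separate problems.

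1. **Trigger.** A mandatory cut on an uncounted event sits beside a rule that tolerates an estimated DLT rate up to 30%, and nothing says which prevails. It is also unstated whether the trigger covers a DLT in Dose Level 1a (whose data are pooled with 1.2 mg/kg) or a Dose Level 1 DLT seen only after escalation.

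2. **Branch.** If the cut is made, dose finding moves to 1.2+0.5, then 2.4+0.5 and 5+0.5. The last two are outside the table, the model and the SAP groups. The gate into them is zero DLTs at Dose Level -1, which is not the 30% criterion that defines the MTD.

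Estimating the MTD is the primary objective. At stake is whether it has a defined estimate if one plausible early event occurs.

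**Working it through.** **Inputs.** From 9.2: F = p^exp(β), β ~ N(0, 1), and the posterior mean of β is put back into F. From 3.1.9: target 30%, 8-week window, 3 to 9 patients per cohort. The likelihood is F for a DLT and 1 − wF for a DLT-free patient with weight w. The Dose Level 1 prior is not printed (the p_i beside Figure 3 are an example), so I assume 11 values from 0.02 to 0.29.

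**Plan's own figure.** The plan gives none for the step-down. The stated 90% interval for exp(β), [0.19, 5.21], is reproduced: exp(±1.65) = 0.192, 5.207 (exp(±1.645) = 0.193, 5.180).

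**Chance that at least one DLT occurs, 1 − (1 − q)^n.** At a true rate q = 10%: 1 − 0.9^3 = 0.27, 1 − 0.9^6 = 0.47, 1 − 0.9^9 = 0.61. At 20%: 0.49, 0.74, 0.87. Read as two or more DLTs, the 10% figures fall to 0.03, 0.11 and 0.23, so the missing count matters. The one-or-more figures also give the chance of failing the zero-DLT gate at Dose Level -1 for the same q and n.

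**Model estimate at Dose Level 1, range over the assumed priors:**

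| Data | w = 1 | w = 0.75 | w = 0.5 |
|---|---|---|---|
| 1/4 | 0.179–0.286 | 0.218–0.368 | 0.262–0.449 |
| 1/6 | 0.132–0.205 | 0.168–0.277 | 0.219–0.378 |
| 2/8 | 0.209–0.273 | 0.265–0.364 | 0.340–0.483 |
| 2/9 | 0.190–0.246 | 0.243–0.331 | 0.319–0.454 |

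At full weight every entry is below 30%, and the observed rates (17% to 25%) pass the 33% gate. At half weight, 2/8 and 2/9 exceed 30% for all 11 priors, 1/4 for 8 and 1/6 for 5.

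*Example, 1/6 complete.* With Dose Level 1 prior 0.095, posterior mean β = −0.256 and exp(β) = 0.774, so the estimate is 0.095^0.774 = 0.162. If 2.4+1 has prior 0.186, its estimate is 0.186^0.774 = 0.272. With priors 0.186 and 0.300, the two estimates are 0.183 and 0.297. In both cases the model points to escalation where the sentence, read as any DLT, halves mogamulizumab. With priors 0.095 and 0.300, 2.4+1 is at 0.394 and the model stays at Dose Level 1. It still does not step down.

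**How often the rules differ when the trigger fires.** A simulation used 4,000 trials per setting. It assumed true Dose Level 1 rates of 5, 10 or 20%, one patient every 1, 2 or 4 weeks, uniform DLT onset, linear weights, and rates at 2.4 and 5 mg/kg of 1.25 and 1.5 times that at Dose Level 1. A Dose Level 1 DLT came before any Dose Level 2 dosing in 9–13%, 18–24% and 32–43% of trials respectively. At the next assignment the model still accepted Dose Level 1 in 0–25% of those (prior 0.095) or 0% (prior 0.186). The upper bound for all trials is 0.43 × 0.25 = 0.11.

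**The branch, item by item:**

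| Combination | Table 6 level | Own p_i in 9.2 | SAP group |
|---|---|---|---|
| 1.2+0.5 | yes (-1) | only if the four p_i are Dose Levels -1, 1, 2, 3 | yes |
| 2.4+0.5 | no | no | no |
| 5+0.5 | no | no | no |

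Neither natural mapping of the four p_i (the four listed PF-05082566 doses, or Dose Levels -1, 1, 2, 3) covers the last two rows. Reusing the p_i by PF-05082566 dose would give 1.2+1 and 1.2+0.5 the same estimate. The DLTs that forced the cut would count fully against the reduced combination, and the model could not tell one combination dose from the other.

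**The case against.** The strongest reply is that the two rules serve different drugs. Section 3.1.9 opens by ruling out mogamulizumab escalation and applying TITE-CRM to PF-05082566. A stricter mogamulizumab step-down is defensible for a combination with no nonclinical toxicology (1.2.2.6). Section 9.2.1 points to 3.1.9 for the criteria, so the softer sentence in 9.2 can be read as describing a contingency. The prose of 3.1.9 does identify 2.4+0.5 and 5+0.5, the SAP exposure formulas allow 0.5 mg/kg, and a group label could be added by amendment.

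Much of this stands. A reader might infer that any DLT at Dose Level 1 sets the rules against each other. It does not, because partial weights usually put the model above 30% as well. A reader might also infer a conflict over whether Dose Level 1 reopens when the estimate later falls. With no mogamulizumab escalation foreseen, the natural answer is that it does not reopen. Nor do the documents support a claim of added patient risk from the step-down, since the error runs towards lower mogamulizumab exposure.

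Three things do not fall away. A deliberately strict rule still needs a count. The 33% gate and the sponsor's override concern escalation and do not supply one. The exposure formulas and the intermediate-dose footnote (attached to the PF-05082566 column, for de-escalation) create no level, prior or estimator for combinations reached by escalating.

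**Conclusion.** The concern holds in two parts of unequal weight.

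The trigger is undefined in count and precedence, and its wording differs between 3.1.9 and 9.2 with SAP 5.1.2. With complete follow-up, data such as 1/6 separate the rules for every assumed prior if any DLT triggers the cut. At the moment of decision, disagreement is uncommon, at most about 11% of trials in the settings simulated. That figure rests on assumed priors, accrual, true rates and linear weights; the plan's adaptive cyclical weights were not modelled.

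The branch is the larger defect and rests on the text alone. Once mogamulizumab is cut and Dose Level -1 is clean, the trial is directed to combinations for which the MTD, defined as a model estimate for a combination dose, has no specified estimate. The zero-DLT gate there is also inconsistent with the 30% target. This should be corrected, although it matters only if the branch is opened.

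**What to change.** 1. **One trigger, with its precedence, worded identically in Protocol 3.1.9, 9.2 and SAP 5.1.2.** Use either a model estimate at Dose Level 1 (pooled with 1a) above 30%, or an explicit DLT count if a stricter step-down is intended. Either is acceptable. Say whether DLTs in Dose Level 1a, and Dose Level 1 DLTs seen after escalation, count.
2. **Specify the branch or delete it.** If it is kept, add Dose Level -1, 2.4+0.5 and 5+0.5 as ordered levels with printed priors and SAP treatment groups, including their order relative to 1.2+1. Replace the zero-DLT gate at Dose Level -1 with the same 30% and 33% rules.

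The cost is wording changes in both documents and a short level-to-prior table, with no extra patients. Re-running the design simulations on the final ladder is optional.
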